## Summary of protocol for post-marketing surveillance (031-101-00116)

## - Aripiprazole for irritability associated with pediatric autism spectrum disorder (ASD) in Japan

Study Title	Abilify special-drug-use-results survey (pediatric autism spectrum disorder: oral
	formulations)
Study Code	031-101-00116
Name of Company	Otsuka Pharmaceutical Co., Ltd.
Responsible party	Office of Surveillance Management, Pharmacovigilance Department
Product Name	ABILIFY Tablets(Aripiprazole), ABILIFY Powder(Aripiprazole), ABILIFY Oral
	Solution(Aripiprazole), ABILIFY OD Tablets (Aripiprazole)
Product, Dose	Drug products investigated:
	ABILIFY Tablets 1mg / 3mg /6mg /12mg
	ABILIFY Powder 1%
	ABILIFY Oral Solution 0.1%
	ABILIFY OD Tablets 3mg /6mg /12mg
	Dosage and Administration:
	The usual starting dose in children (from 6 to 17 years old) is 1 mg of
	aripiprazole per day administered. Maintenance dose are from 1mg to 15 mg per
	day are administrated. The dose may be changed for symptom, The fluctuation of
	dose are restricted to 3mg per day.
Clinical Phase	IV (non-interventional study)
Rationale and	Observational study conducted in Japan is based on the re-examination system and
background	not as a condition of the marketing authorization. This kind of non-interventional
	study is generally imposed to all new drugs to quantify the incidence of adverse
	drug reactions (ADRs), and not requested to identify the safety concerns.
	The re-examination system in Japan is defined by the article 14-4 of the
	Pharmaceutical Affairs Law. During a period of re-examination, the MAH plans
	and conducts post-marketing surveys based on GPSP ordinance. In meantime,
	results from post-marketing surveys are reported periodically to PMDA based on
	Periodic Safety Reports (Article 63 of the Enforcement Regulations of the Law).
Objective	The purpose of this survey is to identify the following safety and efficacy-related
	questions for an observation period of 1 year with use of oral drug of Abilify in the
	routine clinical setting.
Study design	Observational study
	(Multicenter, prospective post-marketing surveillance)
Data source	Not applicable (Primary data collection)
[	1

Population	Pediatric patients in Japan with irritability associated with autism spectrum disorder
	who are planned to be newly started on oral drug of Abilify.
Sample size	300 patients
Study Period	Study period: April 2017 to September 2019 (30 months)
	Enrollment period: April 2017 to June 2018 (15 months)
	End of Data collection: December 2019
Primary end point	For each patient, the observation period is 1 year from the start date of oral drug of
	Abilify.
	For patients who discontinue oral drug of Abilify therapy within 1 year, the
	observation period is to be up to the date of discontinuation of Abilify
	administration.
Methodology	Safety information is collected with the procedure described in applicable SOPs.
	Safety Information is defined as "Any information from any source containing
	information such as:
	Adverse event or suspicion thereof
	• Lack of efficacy
	Overdose/incorrect dosage (accidental or intentional)
	• Abuse/misuse (e.g. patients sharing medication) – even without resulting adverse
	reaction
	Accidental exposure (e.g. child takes parent's medication)
	Medication error
	Withdrawal reactions
	Disease progression/exacerbation of existing disease
	Drug-drug/Drug-food interactions
	• Exposure to drug during pregnancy, where the embryo or fetus may have been
	exposed to medicinal products (either through maternal exposure or transmission
	of a medicinal product via semen following paternal exposure).
	Exposure to drug during lactation (including uneventful)
	Suspected counterfeit product
	• Suspected transfer of infectious disease/agent by the medicinal product concerned.
	· Product Quality Complaint (PQC) with safety related/medically important
	information
	Pediatric use (if not an approved use)
	Occupational exposure
	• Off-label use
	Data entry system for original data: PostMaNet (Ver.4) (an electronic data

	capturing system of Fujitsu FIP Corporation)
	Forwards Safety Information from any source to the Local Safety Manager (LSM)
	or appropriate local PV Representative within 24 hours of awareness or the next
	working day in the case of receipt the day prior to or during a weekend, but no later
	than 3 calendar days for reporting to the Global Case Receipt Mailbox.
	Type of CRF: eCRF
Reconciliation	The reconciliation of the serious and non-serious AEs between PV database (Argus)
	and study database is going to be performed on a monthly basis and at the end of the
	study.
Final study report	The FSR will be finalized within one year of the end of data collection
	(30 December 2020).

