1.2. Timing of assessment and acceptable ranges

Timing of assessment is Baseline, Week 4, Week 8, Week 16, Week 24, Week 52, End-point (LOCF). If more than one data is present within each period, calculate the absolute difference in days from the reference day and employ the smallest absolute value as the data for the time of assessment. If the absolute value is the same, data for the later assessment date will be employed. In addition, data evaluated after the 8th day of the last dose of drug will not be included. Day 1 is the starting day of drug administration for the elapsed days from the starting day of drug administration.

Time point	Record Date	Acceptable range	
Baseline	First dose	Day -30 to Day 1	
Week 4	Day 28	≥Day 15, < Day 43	
Week 8	Day 56	≥Day 43, < Day 71	

Time point	Record Date	Acceptable range	
Week 16	Day 112	≥Day 85, < Day 141	
Week 24	Day 168	≥Day 141, < Day 197	
Week 52	Day 364	≥Day 337, < Day 393	
End-point (LOCF)	Date ^{a)} closest to Day 364	-	

a) Data outside the acceptable range will also be included. However, the all effectiveness measures, which were assessed over 7 days after last dose or after Day 393 should be excluded.

2. Software for analysis

The following software is used for the analysis.

- SAS 9.2 or later (SAS Institute Japan Ltd.)
- Microsoft Office Excel 2007 or later

3. Analysis

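### Safety observation closes on the day the drug is stopped and no later follow-up is described, so early post-stop reactions would probably be under-counted

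*Protocol*

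**What the plan says.** The Protocol's Primary end point row sets two observation rules. The general one is "For each patient, the observation period is 1 year from the start date of oral drug of" Abilify. For a child who stops within the year, the "observation period is to be up to the date of discontinuation of Abilify" administration.

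The Methodology row defines safety information by a long open list in which "Withdrawal reactions" is one entry. It adds that "Safety information is collected with the procedure described in applicable SOPs"; those SOPs are not reproduced. Such information is to be forwarded to pharmacovigilance promptly after someone becomes aware of it, whatever its source, and no time limit relative to the last dose is given. The Reconciliation row compares serious and non-serious events between the pharmacovigilance and study databases monthly and at study end.

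For assessments, SAP 1.2 states that "data evaluated after the 8th day of the last dose of drug will not be included". SAP 1.1 and the footnote to the SAP 1.2 table express the cut-off for effectiveness measures as more than 7 days after the last dose. SAP 3.3 and 3.3.1.1 call for counts and incidence of adverse events. They give no onset window and no separate handling of events after stopping.

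**The concern.** A reaction to stopping a drug begins, by its nature, after the drug is stopped. Under the observation rule, the site's planned follow-up of that child has then already ended. A child who reacts a few days later enters the data only if a parent or physician volunteers the information. The Protocol's Rationale row says surveys of this kind are done to quantify how often adverse drug reactions occur, so a rule that ends observation at this moment bears on the survey's purpose. At stake is how the report is read: a low count of early post-stop events could reflect the collection rule and not the drug, and nothing in the planned tables would tell the two apart.

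**Working it through.** The plan states no figure to reproduce on this point. The check compares the rules, then tests whether the timetable leaves room for a short follow-up.

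**1. Windows after stopping** (treating the discontinuation date and the date of last dose as the same day)

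| Data | Source | Time after stopping |
|---|---|---|
| Any planned observation, early stoppers | Protocol, Primary end point row | 0 days |
| Effectiveness ratings accepted for analysis | SAP 1.1, SAP 1.2 and footnote | up to 7 days |
| Adverse events tabulated | SAP 3.3, 3.3.1.1 | no window stated |
| Unsolicited safety reports | Protocol, Methodology row | no limit stated |

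The 8th-day wording in SAP 1.2 agrees with the 7-day wording elsewhere if the day of the last dose is counted as the first day.

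**2. An event and a rating on day 5 after stopping.** Both lie outside the Protocol's observation period. The SAP explicitly admits the rating if it was recorded. It is silent on the event, so neither document says whether an event that reaches the pharmacovigilance database this way belongs in the SAP 3.3.1.1 numerator.

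**3. What reconciliation can do.** It compares events already reported to one database or the other. It cannot find an event nobody reported.

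**4. Timetable.** Assume a child starts on the last enrolment day, 30 June 2018. One year ends on 29 June 2019.
- To the end of the study period (30 September 2019): 1 + 31 + 31 + 30 = 93 days.
- To the end of data collection (31 December 2019): 93 + 31 + 30 + 31 = 185 days.
- After a 7-day extension: 93 − 7 = 86 days and 185 − 7 = 178 days.

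The calendar does not prevent a 7-day extension.

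**5. Would a short follow-up be informative?** The documents give no rates, so these are assumptions: 10% to 50% of the 300 stop (30 to 150 children), and all of them are asked. The chance of seeing at least one reaction is 1 − (1 − p)^n.
- True rate 1%: 1 − 0.99^30 = 26% to 1 − 0.99^150 = 78%.
- True rate 5%: 1 − 0.95^30 = 79% to 1 − 0.95^150, over 99%.

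If none were seen, the upper 95% bound among those asked, 1 − 0.05^(1/n), would be 9.5% for n = 30 and 2.0% for n = 150. How reassuring a zero is depends on how many stoppers were asked, so that number has to be reported.

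**The case against.** The case on the other side is substantial.

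- **The list is generic.** Withdrawal reactions sit beside counterfeit product, occupational exposure and quality complaints in a definition of what must be forwarded. They are not a survey endpoint. The Rationale row also says such studies are not requested in order to identify safety concerns, and the objective concerns use of the drug. This stands. A reader might infer that the survey cannot observe a risk it set out to measure; the documents do not support that.
- **The reporting route stays open.** Forwarding has no time limit, reconciliation runs to study end, and SAP 3.3 excludes no recorded post-stop event. This stands against any claim that such events are shut out. It does not supply active ascertainment.
- **The SOPs and eCRF content are not shown.** They may ask about events after stopping. This limits certainty. If they do, they still need reconciling with an observation rule that ends on the stop date.
- **The efficacy contrast is uneven.** It sets an SAP acceptance window against a Protocol observation rule. This is right: it is a mismatch between documents, not a rule that favours efficacy over safety.
- **Some withdrawal reactions fall inside the window.** Dose changes on treatment are allowed, so a reaction to a reduction could be observed. This is true, but it does not cover reactions to stopping altogether.
- **The remedy is imperfect.** Seven days is borrowed from an effectiveness rule, and no contact after stopping is guaranteed. This stands too, and is why the denominator must be restricted to those contacted.

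**Conclusion.** The point holds as a probable under-count. Followed as written, the observation rule gives early stoppers 0 days of planned safety observation after discontinuation, against up to 7 days for effectiveness data. Reactions beginning in that interval would rest on unsolicited reports with no defined denominator. This does not invalidate the on-treatment incidence, but it should be corrected because the survey's purpose is incidence.

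The size of the under-count cannot be derived from the documents, and two tempting numbers should not be used:
- Assuming that 20% to 50% of 300 stop and 2% to 10% of those react gives 60 × 0.02 = 1.2 to 150 × 0.10 = 15 children. Both rates are assumptions, the range is more than tenfold, and reading it as the loss presumes every such reaction goes unreported.
- A reader might infer that zero reports among 300 would rule out a rate above 1 − 0.05^(1/300) = 0.99%. The SAP plans no such bound, and 300 is the wrong denominator because only children who stop are at risk.

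The conclusion assumes that the SOPs and eCRF, which are not shown, do not already prescribe collection after the last dose.

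**What to change.** Make three linked changes, for adverse events only:

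1. **Protocol, Primary end point row:** for patients who stop within the year, extend adverse event collection to 7 days after the last dose, matching the SAP's existing allowance for effectiveness data. If an SOP already sets a post-stop window, state it here and reconcile the two.
2. **eCRF:** add one item asking for events since the last dose, answered at the next routine contact if there is one.
3. **SAP 3.3.1.1:** tabulate events with onset after the last dose in a separate column. Use as denominator the number of discontinued patients who had a post-stop contact. The on-treatment incidence stays as planned.

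The cost is one sentence, one eCRF item and one table column, with no added visit or procedure, which suits a non-interventional survey. There are two downsides. Some post-stop events will reflect a new treatment or the underlying condition, hence the separate column. Ascertainment will also be incomplete where no contact follows, and the report should say so.

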Summary of statistical analysis plan (SAP) for post-marketing surveillance (031-101-00116) - Aripiprazole for irritability associated with pediatric autism spectrum disorder (ASD) in Japan

- 1. Definition
 - 1.1. Patient disposition

Patient disposition	Definition		
Enrolled	Enrolled cases.		
Case report failures	Case reports were unavailable among the enrolled cases.		
Case reports collected	Case reports were collected and locked the data among the enrolled cases.		
Exclusion criteria for	1. Treatment not administered		
safety analysis	2. Lost to follow-up		
	3. First dose before registration		
	4. Others		
Safety analysis	Cases do not meet exclusion criteria for safety analysis among the case		
	reports collected.		
Exclusion criteria for	1. Registration after Day 15		
efficacy analysis	2. Other indications (not for irritability associated with pediatric ASD)		
	3. Assessment failures (all effectiveness measures were not assessed		
	after treatment)		
	4. Others (all effectiveness measures were assessed over 7 days after		
	last dose or after Day 393, overdose: > 15 mg/day)		
Efficacy analysis	Cases do not meet exclusion criteria for efficacy analysis among the		
	safety analysis.		

1.2. Timing of assessment and acceptable ranges

Timing of assessment is Baseline, Week 4, Week 8, Week 16, Week 24, Week 52, End-point (LOCF). If more than one data is present within each period, calculate the absolute difference in days from the reference day and employ the smallest absolute value as the data for the time of assessment. If the absolute value is the same, data for the later assessment date will be employed. In addition, data evaluated after the 8th day of the last dose of drug will not be included. Day 1 is the starting day of drug administration for the elapsed days from the starting day of drug administration.

Time point	Record Date	Acceptable range	
Baseline	First dose	Day -30 to Day 1	
Week 4	Day 28	≥Day 15, < Day 43	
Week 8	Day 56	≥Day 43, < Day 71	

Time point	Record Date	Acceptable range	
Week 16	Day 112	≥Day 85, < Day 141	
Week 24	Day 168	≥Day 141, < Day 197	
Week 52	Day 364	≥Day 337, < Day 393	
End-point (LOCF)	Date ^{a)} closest to Day 364	-	

a) Data outside the acceptable range will also be included. However, the all effectiveness measures, which were assessed over 7 days after last dose or after Day 393 should be excluded.

2. Software for analysis

The following software is used for the analysis.

- SAS 9.2 or later (SAS Institute Japan Ltd.)
- Microsoft Office Excel 2007 or later

3. Analysis

3.1.1. Patient disposition

Prepare the Patient disposition figure.

3.2. Patient demographics

The following items will be tabulated in Safety analysis sample:

Item	Classification	Tabulation and analysis method
Gender	Male and Female	Frequency tabulation
Age	 - < 6 years old - ≥ 6 years old, < 13 years old - ≥ 13 years old, < 18 years old - ≥ 18 years old - Unknown 	Summary statistics, frequency tabulation
Baseline ABC-J Score	Baseline Subscale Score [Irritability Subscale Score]	Summary statistics

3.3. Safety analysis

Safety analyses are for Safety analysis sample.

- 3.3.1. Adverse events
 - 1) Adverse events will be coded according to the latest version of MedDRA/J at the time of analysis or its previous version. SOC and PT will be tabulated by case number.
 - 2) If more than one adverse event (PT) is observed within the same case, the data will be

summarized as one subject.

- 3) If more than one adverse event (SOC) is observed within the same case, the data will be summarized as one subject.
 - 3.3.1.1. Frequency of adverse reactions

The number of cases with adverse events and the incidence of adverse events will be calculated by serious/non-serious and total. In addition, the frequency by SOC and PT is tabulated.

3.4. Efficacy analysis

Efficacy analyses are for Efficacy analysis sample.

Observed Case (OC) will be used for the analysis of each assessment time point. Last Observation Carried Forward (LOCF) is also used to analyze End-point.

3.4.1. ABC-J

Efficacy analysis sample consisted of all participants who received at least one dose of study medication and have Baseline and at least one Post-Baseline efficacy evaluation.

1) Irritability Subscale Score

The total scores for 15 items in item No. 2, 4, 8, 10, 14, 19, 25, 29, 34, 36, 41, 47, 50, 52 and 57 of ABC-J shall be calculated.

However, if at least one missing value is observed during the observation period, the total score will not be calculated.

Summary statistics will be calculated for the changes in subscale scores by time of assessment.

End of document
